One limitation of the CO-STAR study is that inclusion in this study required participants being on stable OST therapy prior to study entry. As such, only 59% of the total study population tested positive for illicit drugs at the time of treatment initiation. Among people enrolled in the 3YFU study, injecting drug use in the past 6 months was only reported by 25% of participants. Further, this study used an innovative adherence reminder device, which may have led to improved outcomes in this population. As such, further data is needed on responses to elbasvir/grazoprevir among recent PWID and people receiving OST in the “real-world”. In addition, long-term follow-up to better characterize HCV reinfection in those with recent injecting drug use and successful therapy is essential.

Australia is an ideal setting for a study to evaluate elbasvir/grazoprevir therapy among recent PWID. First, Australia has a strong foundation of health services for HCV testing (>80% of PWID have been HCV tested and diagnosed) and care among PWID and people receiving OST. Second, there is a well-established network of clinical sites experienced in clinical trial research. Third, Australia has a high coverage of NSP and OST services for PWID, which could act in combination with HCV treatment scale-up to achieve greater prevention benefits. Lastly, Australia is the first country in the world to have broad access to government-funded interferon-free DAA HCV therapies without disease-based and drug and alcohol use-based restrictions and including specialist and general practitioner prescribing. Within the context of an HCV treatment scale-up project, this would enable the evaluation of elbasvir/grazoprevir for people with HCV genotype 1 or 4 and recent injecting drug use or receiving OST.

Drug and alcohol clinics and primary health care clinics are logical venues for expanding HCV care, given the large burden of HCV and an existing framework for the provision of care for PWID. These settings are ideal for a study to evaluate HCV treatment scale-up among PWID with recent injecting drug use or receiving OST in the tertiary, drug and alcohol and primary health care settings. This project will build on the existing clinical capacity at these clinics and utilize the internationally leading Kirby Institute Viral Hepatitis Clinical Research Program expertise and clinical research operational capacity.

2. Study objectives

Primary Hypothesis

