
Week 8 (+/- 7 days)

- LFTs – ALT only
- Pregnancy test (females of child bearing potential only)
- Serious Adverse Events
- Research specimen collection (EDTA plasma)
- Study questionnaire (Adherence)

End of Treatment (ETR) - Week 12 (+/-14 days)

- Qualitative HCV RNA (where available, otherwise quantitative), (Local laboratory)
- LFTs, FBC and biochemistry
- Pregnancy test (females of child bearing potential only)
- Serious Adverse Events
- Concomitant medication
- Study questionnaires (Abbreviated Behavioural, Adherence, and EQ-5D)
- Research specimen collection (EDTA plasma)

Post Treatment Follow-up Visits

Post Treatment Week 12 (SVR12) - Week 24 (+/- 14 days)

- Qualitative HCV RNA (Where available, otherwise quantitative) (Local laboratory)
- LFTs, FBC and biochemistry
- Pregnancy test (females of child bearing potential only) (at 14 days post end of treatment – home test allowed)
- Serious Adverse Events (up to week 16 (SVR4) only)
- Study questionnaires (Abbreviated Behavioural and EQ-5D)
- Research specimen collection (EDTA plasma)
- Finger-stick point-of-care HCV RNA testing (Sub-study sites only)

Post Treatment Weeks 36 (FU1), 48 (FU2), 60 (FU3), 84 (FU4), 108 (FU5), 132 (FU6) and 156 (FU7) (+/- 14 days)

- Qualitative HCV RNA (Where available, otherwise quantitative) (Local laboratory)
- Study questionnaires (Abbreviated Behavioural)
- Research specimen collection (EDTA plasma)
- Finger-stick point-of-care HCV RNA testing (Sub-study sites only)

If a patient has suspected viral relapse or HCV reinfection HCV RNA sequencing will be performed. No additional sample is required.

Monitoring of HBV reactivation

At screening, all patients will be tested for evidence of current (Hepatitis B surface antigen positive) and prior (anti-Hepatitis B core antibody positive) HBV infection before initiation of treatment. Patients with current HBV infection will be excluded. Patients with evidence of prior HBV infection only will be enrolled.

Patients with evidence of prior HBV infection will be monitored for HBV reactivation and hepatitis flare during HCV treatment and post-treatment follow-up. LFTs will be performed 4-weekly during treatment. In the setting of a clinically significant ALT elevation or symptoms and signs of acute hepatitis, HBV DNA testing will be performed to assess for reactivation. Appropriate management for HBV infection will be initiated by the site investigator as clinically indicated.

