6.3 Linkage of data (optional)

Participants are invited to consent to link their data collected during the DARLO-C study with routinely collected data from a range of population Health and Incarceration databases and registers.

The collection of participant names, date of birth, sex, and post code in DARLO-C is essential for accurate data linkage. Participant data will be linked to a variety of health variables including information on hepatitis C notifications, HIV/AIDS notifications, use of hepatitis services, use of prescription medication (including hepatitis C treatment), OST, incarceration, hospitalizations, emergency department use, cancer, and mortality through the New South Wales Centre for Health Record Linkage (www.cherel.org.au), and the Australian Institute of Health and Welfare (www.aihw.gov.au). Linkage will be both retrospective and prospective, with the time period covered dependent on the properties of the specific data set. Approval from the NSW Population and Health Services Research Ethics Committee, and all other required Human Research Ethics Committees will be sought prior to any data linkage being performed.

Participants are given the option to opt out of the health and incarceration data linkage component of this study on the Participant Consent Form. Participants not wishing to have their data used in the data linkage studies may still enroll in DARLO-C.

7. Recording and reporting Adverse Events (AEs)

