9.3 Future use of biological samples

After the samples have been analysed for the study endpoints as specified in the protocol, remaining samples will be stored for use in future Human Research Ethics Committee approved hepatitis C related research. Additional consent will not be sought for this storage and future use. It is not optional. Subjects not wishing to have their samples stored or used in future hepatitis C related research will not be eligible to participate in this study.

10. Statistics

The statistical team and investigators at the Kirby Institute will be responsible for analysing the study data.

Primary Objective: To evaluate the proportion of patients with undetectable HCV RNA at 12 weeks post end of treatment (SVR12) following elbasvir/grazoprevir therapy among PWID with recent injecting drug use or receiving OST and chronic HCV genotype 1 or 4 infection and evaluate demographic and clinical predictors of non-response.

Hypothesis: *Elbasvir/grazoprevir therapy will lead to SVR12 >90% among PWID with recent injecting drug use or receiving OST and chronic HCV genotype 1 or 4 infection.*

Outcome: The primary endpoint for this aim is the proportion of participants with a treatment response (measured by SVR, undetectable HCV RNA 12 weeks after the completion of therapy).

Statistical analysis: The proportion of people with a response to HCV therapy will be evaluated. Factors associated with treatment response (as measured by SVR) will be assessed by univariate and multivariate logistic regression analyses. Factors hypothesized to be associated with HCV treatment response will be assessed including: sociodemographic factors (housing and education), injecting behaviours (recent injecting drug use prior to and during therapy and type of drug injected), and clinical factors (opioid substitution treatment, HCV genotype, fibrosis stage).

Sample Size: Assuming an overall SVR of 90% (135 of 150), the 95% confidence interval around this estimate will be 84.0% to 94.3%. This study will have robust power to examine the effect of treatment setting on SVR: e.g. 80% power to detect an odds ratio of 0.39 or 2.59 or more extreme (with alpha=0.05) for a variable that is 50% prevalent.

Secondary Objective: Estimate incidence and predictors of HCV reinfection after successful elbasvir/grazoprevir.

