Hypothesis 2.1: The incidence of HCV reinfection following successful elbasvir/grazoprevir therapy will be <8 per 100 p-yrs among people with recent injecting drug use or receiving OST.

Hypothesis 2.2: HCV reinfection will be associated with ongoing \geq daily injecting drug use, and needle and syringe borrowing. OST and high-coverage access to needle and syringes will be associated with reduced HCV reinfection.

Outcome: Incidence of HCV reinfection following successful elbasvir/grazoprevir therapy.

Statistical analysis: Rates of HCV reinfection will be calculated using person-time of observation. The estimated date of reinfection will be calculated as the midpoint between the dates of the last undetectable HCV RNA test and the first detectable HCV RNA test at the time of HCV reinfection. Time at risk will commence at the date of undetectable HCV RNA at end of treatment and end at the first of estimated date of re-infection, death, loss-to-follow up or end of study. Confidence intervals for rates will be calculated using a Poisson distribution.

Cox proportional hazards analyses (or other appropriate regression models) will be used to estimate crude and adjusted hazard ratios and corresponding 95%CI to evaluate factors associated with reinfection. Factors hypothesised to be associated with reinfection include demographic factors (age, sex), injecting behaviours (current injecting drug use, daily injecting, type of drug injected, injecting equipment borrowing), use of needle and syringe programs, and opioid substitution treatment with time-updated co-variables.

Sample Size: Overall, based on previous reports of HCV reinfection among current PWID³², and assuming loss to follow-up is 20% per year, it is estimated that the overall reinfection rate will be 8/100 p-yrs (95%CI 5.3, 11.4; 337 p-yrs of follow-up; 27 reinfections). Overall (135 with successful therapy, 27 reinfections), we will have 80% power to detect a hazards ratio (HR) of 2.94 or greater (with alpha=0.05) for a variable 50% prevalent (e.g. ongoing injecting drug use).

Collateral research

Evaluation of HCV phylogenetics

All participants enrolled in this study with available plasma samples at screening or baseline (HCV RNA detectable) will be sequenced for HCV RNA for evaluation of HCV phylogenetics.

Evaluation of HCV re-infection

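### No scheduled visit after Week 12 explicitly records hepatitis C treatment or HCV RNA results from outside the study, and the reinfection analysis has no rule for retreatment

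*Combined protocol and SAP*

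**What the plan says.** **Reinfection analysis (Section 10, Secondary Objective).** "Time at risk will commence at the date of undetectable HCV RNA at end of treatment", and it is to "end at the first of estimated date of re-infection, death, loss-to-follow up or end of study". The reinfection date is the "midpoint between the dates of the last undetectable HCV RNA test and the first detectable HCV RNA test". HCV retreatment does not appear, either as an event that ends time at risk or as a case to be classified.

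**SVR12 (Section 10, Primary Objective).** The outcome is "undetectable HCV RNA 12 weeks after the completion of therapy". No rule covers another HCV antiviral taken before that sample.

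**Data collected (Section 6.1 and the Schedule of Assessments).** "Concomitant medication" is listed at Screening, Baseline and Week 12. It is absent at Week 24 and at the visits headed "Post Treatment Weeks 36 (FU1), 48 (FU2), 60 (FU3), 84 (FU4), 108 (FU5), 132 (FU6) and 156 (FU7". Those visits have an HCV RNA test, the abbreviated behavioural survey, a research sample and, at sub-study sites, a finger-stick test. Week 24 adds EQ-5D, routine bloods and safety items. Section 6.2 describes the full behavioural survey as covering HIV and drug treatment history; it does not name HCV retreatment and does not itemise the abbreviated form.

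**Linkage (Section 6.3).** The variables to be linked include "use of prescription medication (including hepatitis C treatment". Participants may opt out, and further ethics approval is required.

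**Setting (Section 1).** Australia is described as having "broad access to government-funded interferon-free DAA HCV therapies without disease-based and drug and alcohol use-based restrictions", with general practitioner prescribing.

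**The concern.** The secondary endpoint is a rate of first reinfection over about three years in people who, in this setting, may be tested and treated outside the study clinics. Up to Week 60 the study tests are 12 weeks apart; after that they are 24 weeks apart. If someone is reinfected after one test, is diagnosed and treated elsewhere, and is undetectable at the next test, the study series shows two undetectable results and no event. The person stays in the denominator, including the time infected and the time on treatment. A participant who misses a visit and later returns undetectable is in the same position, over a longer gap. The plan itself assumes 20% annual loss, so irregular attendance is to be expected.

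The error runs one way: events are lost and person-time is kept, which lowers the rate. The SVR12 counterpart also runs in the favourable direction, because suppression achieved on another drug would be credited to elbasvir/grazoprevir. If dates and results are not collected at the visits, an analyst cannot fully recover them later, least of all for participants who opted out of linkage.

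**Working it through.** **1. The plan's own figures.** 27 reinfections over 337 person-years is 27/337 = 8.01 per 100, as stated. The detectable hazard ratio (Schoenfeld, two-sided alpha 0.05, 80% power, 50% prevalence) is exp[(1.960 + 0.842)/√(27 × 0.25)] = 2.94, as stated. For SVR12, 135/150 gives an exact 95% interval of 84.0% to 94.3%, as stated. The exact Poisson interval for 27/337 is 5.3 to 11.7, against the stated 5.3 to 11.4. That is a separate matter and does not affect what follows.

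**2. Where a reinfection could pass unseen.** Let L be the weeks from infection to undetectable RNA on outside treatment. If infection is uniform over a gap of G weeks, the fraction of outside-treated reinfections missed is (G − L)/G, or zero if L is at least G. With L of 12 weeks or more, nothing is missed in a nominal 12-week gap, so the 24-week gaps from Week 60 to Week 156 matter most.

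**3. Share of person-time in those gaps.** With 135 participants at risk from Week 12 and 20% annual loss taken as continuous (hazard −ln 0.8 = 0.223 per year):
- Weeks 12 to 60: 112.6 person-years
- Weeks 60 to 156: 166.2 person-years
- Share: 166.2/278.9 = 0.596

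This total is below the plan's 337 because loss is continuous and follow-up stops at Week 156. Only the share is used.

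**4. Fraction of all reinfections missed** = 0.596 × q × (24 − L)/24, where q is the proportion treated outside the study before the next study test. Neither q nor L is in the documents; both are assumptions. A true rate of 8.0 would read 8.0 × (1 − fraction missed).

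| L (weeks) | q = 20%: missed; events of 27; rate | q = 50%: missed; events of 27; rate |
|---|---|---|
| 12 | 6.0%; 1.6; 7.5 | 14.9%; 4.0; 6.8 |
| 16 | 4.0%; 1.1; 7.7 | 9.9%; 2.7; 7.2 |
| 20 | 2.0%; 0.5; 7.8 | 5.0%; 1.3; 7.6 |
| 24 or more | 0; 0; 8.0 | 0; 0; 8.0 |

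The table uses nominal gaps. The ±14-day windows can stretch 24 weeks to 28. A skipped visit makes the gap 48 weeks, where (48 − 12)/48 = 75% of outside-treated cases would be missed at L = 12 and 50% at L = 24.

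**5. Effect on conclusions.** Losing 4 of 27 events gives 23/337 = 6.8 (exact Poisson 95% interval 4.3 to 10.2), and power at a hazard ratio of 2.94 falls from 80% to 73%. An upper limit below 8 at 337 person-years needs 16 events or fewer (16 gives 7.7; 17 gives 8.1), so the loss of 1 to 4 events from 27 would not produce one.

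**6. SVR12.** Each misclassified failure adds 1/150 = 0.67 percentage points: 135/150 = 90.0% becomes 136/150 = 90.7%, and three make 138/150 = 92.0%. A lower limit above 90% needs 143/150.

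**The case against.** Several counter-arguments stand, and they limit the point.

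- **Retreatment is not wholly unrecorded.** A reader might infer that the study has no source for it after Week 12. The documents do not support that. Section 6.3 plans retrospective and prospective linkage to hepatitis C treatment, Section 12.2 plans periodic linkage to registries, and the abbreviated survey's items are not shown. What can be shown is that no scheduled visit explicitly records it and that Section 10 does not use the linked data.
- **The dating rule is not confined to study tests.** It refers to the first detectable test without restriction, and local follow-up RNA testing is footnoted as standard of care. An outside positive that reaches the site already fits. The loss needs infection, diagnosis, treatment and suppression between two tests, with the positive result never captured. A reinfection found at a visit ends time at risk, so later retreatment does not matter.
- **The protocol does not say that participants can obtain a second course.** Section 1 describes broad access to therapy; extending this to retreatment is an inference.
- **The SVR12 route is narrow.** No RNA test is scheduled between Weeks 12 and 24, and a drug started before the Week 12 visit should appear in that visit's medication record. It mainly concerns failures known by Week 12 and early stoppers.
- **Crossing 8 or 90% by one case is partly an artefact.** The planning values sit exactly on those thresholds.

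What remains is that nothing schedules the collection of outside treatment or results at follow-up visits, linkage is incomplete by design, and the analysis text is silent on retreatment for both endpoints.

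**Conclusion.** The gap is real and modest. After Week 12 no scheduled visit explicitly captures outside HCV antivirals or RNA results, and Section 10 does not say how retreatment affects time at risk or SVR12. Any resulting bias lowers the reinfection rate and raises SVR12.

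The size cannot be estimated from the documents. It ranges from about 0% of reinfections missed (24 weeks or more from infection to suppression) to about 15% (12 weeks, half treated elsewhere), so a true 8.0 would read about 6.8 to 8.0 per 100 person-years. This rests on uniform infection within intervals, nominal visit gaps, 20% continuous annual loss, and assumed values of q and L. Skipped visits would add to it.

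A reader might conclude that the reinfection hypothesis would be falsely confirmed or that SVR12 is materially inflated. The documents support neither: the shift lies well inside the planned interval, a conclusion based on the confidence interval would rarely change, and the SVR12 route affects few participants. The case for acting is that the data are cheap to collect now and hard to recover later.

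**What to change.** 1. At Week 24 and FU1 to FU7, and when a participant returns after missed visits, record any HCV antiviral started since the last visit (drug, start date) and any available HCV RNA result obtained outside the study.
2. In Section 10, state that an outside detectable result counts as the first detectable test for the midpoint rule. Where retreatment has no available RNA result or sequence, end time at risk no later than its start, and report the rate twice: with these cases counted as recurrence events and with them censored. Both are needed, because censoring alone still drops the likely event. The abbreviations list also defines reinfection by a distinct strain, which an unsequenced case cannot show.
3. In the SVR12 analysis, count a non-study HCV antiviral started before the SVR12 sample as non-response.
4. Prespecify linked prescription data, where consented and approved, as a check on items 1 to 3.

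The cost is one added form item, some effort to obtain outside results, and a few lines of analysis text. No extra visit, sample or participant is needed. The reported rate may be slightly less favourable.

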All participants with an ETR will be followed for up to three years post-ETR to assess HCV reinfection. Participants with viral recurrence (detectable HCV RNA following HCV virological suppression, reinfection rate: 8/100 person years, estimated n=27 x 2 samples=54 total samples) will be identified and available follow-up plasma samples assessed for re-infection.

The sensitivity and specificity of the Xpert® HCV Viral Load point-of-care test for detection of HCV RNA in plasma samples collected via venepuncture and capillary whole-blood samples collected by finger-stick will be assessed using both detectable and quantifiable thresholds (limit of quantification >10 IU/mL) for each assay compared to the local laboratory HCV RNA assay in plasma as the gold standard. A Bland-Altman difference plot will be generated to assess bias and agreement measurements, including limits of agreement, between the quantification of HCV by Xpert® HCV Viral Load both sample types, compared to the local laboratory HCV RNA assay in plasma.

11. Data Safety and Monitoring Board (DSMB).

A Data Safety Monitoring Board will not be used for this study as the drug is being prescribed and supplied according to indication via the PBS.

The study Medical Monitor, A/[name] will oversee all serious adverse events for DARLO-C. A/[name] is independent of the study project management team and Protocol Steering Committee. A/[name] is also a clinician at St Vincent's Hospital which is one of the recruiting sites. Should an SAE occur in a patient under A/[name] care the project team will seek an independent review of the SAE from a suitably qualified independent Infectious Diseases Specialist or Hepatologist.

12. Data collection, source documents and record retention

The Principal Investigator and the institution where the study will be conducted will permit study-related monitoring, audits, ethics committee review and regulatory inspection providing direct access to source documents.

Data will be collected on study specific electronic or paper copy case record forms. The Principal Investigator is responsible for ensuring the data collected are complete, accurate and recorded in a timely manner.

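### Reinfection planning figures: the upper confidence limit is 11.7, not 11.4, under the plan's Poisson method, and 337 person-years with 27 events does not follow from 135 responders with 20% annual loss

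*Combined protocol and SAP*

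**What the plan says.** All of this is in Section 10 (Statistics) of the combined protocol and SAP.

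- Primary Objective, Sample Size: the number of responders comes from "Assuming an overall SVR of 90% (135 of 150").
- Secondary Objective, Statistical analysis: time at risk starts when HCV RNA is undetectable at end of treatment, and is to "end at the first of estimated date of re-infection, death, loss-to-follow up or end of study". On intervals: "Confidence intervals for rates will be calculated using a Poisson distribution".
- Secondary Objective, Sample Size: "assuming loss to follow-up is 20% per year", the plan expects "8/100 p-yrs (95%CI 5.3, 11.4; 337 p-yrs of follow-up; 27 reinfections"). It continues "Overall (135 with successful therapy, 27 reinfections"), "we will have 80% power to detect a hazards ratio (HR) of 2.94 or greater", with alpha 0.05 and a variable that is 50% prevalent.
- Evaluation of HCV re-infection: "All participants with an ETR will be followed for up to three years post-ETR to assess HCV reinfection". The count of 27 is used again there to plan sample numbers.

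No derivation of the 337 person-years is given. The plan does not say whether the 20% applies to those still under follow-up or to the original cohort, or whether losses fall through the year or at its end.

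**The concern.** The printed interval should be what the named method gives for the printed events and person-years, and it is not.

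The person-years also look too high. 337 / 135 = 2.50 years per responder, out of a maximum of three. That is hard to reach when a fifth are lost each year and reinfected participants also stop contributing time.

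The event count carries the planning of the secondary objective. It sets the stated precision for Hypothesis 2.1 (rate below 8 per 100 person-years) and the stated power for Hypothesis 2.2 (predictors of reinfection). If 27 is too high, both are less favourable than written.

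**Working it through.** **Inputs (Section 10).** N = 135; reinfection rate 0.08 per year; loss 20% per year; risk starts at end of treatment and stops at reinfection, loss or end of study; maximum three years; alpha 0.05 (taken as two-sided); prevalence 50%. Deaths are not modelled; including them would lower the totals.

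**What reproduces.** 0.08 × 337 = 26.96, so 27 events. The detectable hazard ratio at 80% power is exp(2.8016 / √(D/4)), where 2.8016 = 1.9600 + 0.8416. With D = 27 this is exp(2.8016 / 2.598) = 2.94. The hazard ratio is therefore right for 27 events.

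**Confidence interval, 27 events in 337 person-years.**
- Exact Poisson lower limit: χ²(0.025; 54 df) / 2 / 337 = 5.28 per 100.
- Exact Poisson upper limit: χ²(0.975; 56 df) / 2 / 337 = 11.66 per 100.
- Other Poisson-type upper limits: log-normal, Byar and score round to 11.7; mid-P and Jeffreys give 11.5; square-root 11.3; Wald 11.0. None gives the pair 5.3 and 11.4.
- Exact binomial for 27 out of 337: 5.35 to 11.44, which matches the printed limits.

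**Person-years with 135 at risk and the stop at reinfection.** Person-years = 135 × ∫₀³ S(t) exp(−0.08t) dt, where S(t) is the proportion not lost. Events = 0.08 × person-years.

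| How the 20% is applied | Person-years | Events |
|---|---|---|
| Of original cohort, spread over the year | 256.4 | 20.5 |
| Of those remaining, spread: 135 × (1 − e^(−0.3031×3)) / 0.3031, where 0.3031 = −ln 0.8 + 0.08 | 266.0 | 21.3 |
| Of those remaining, spread, no loss in the first 12 weeks | 279.2 | 22.3 |
| Of original cohort, at year-end | 291.9 | 23.4 |
| Of those remaining, at year-end: 135 × 0.96105 × (1 + 0.73849 + 0.54537) | 296.3 | 23.7 |
| Annual table, 20% and 8% both removed at year-end: 135 × (1 + 0.72 + 0.5184) | 302.2 | 24.2 |
| Of those remaining, at year-end, no loss in the first 12 weeks | 306.2 | 24.5 |
| Annual table, 8% taken from those not lost (0.8 × 0.92 = 0.736): 135 × (1 + 0.736 + 0.5417) | 307.5 | 24.6 |

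In the year-end row, 0.96105 = (1 − e^(−0.08)) / 0.08 and 0.73849 = 0.8 × e^(−0.08). None of these conventions reaches 337 or 27.

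**Consequences.** Power at a hazard ratio of 2.94 is Φ(√(D/4) × ln 2.94 − 1.96).

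| Events D | Power at 2.94 | Detectable hazard ratio, 80% power |
|---|---|---|
| 27 (plan) | 80% | 2.94 |
| 24.6 | 76% | 3.09 |
| 23.7 | 75% | 3.16 |
| 21.3 | 70% | 3.37 |
| 20.5 | 68% | 3.45 |

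Exact Poisson intervals: 4.9 to 12.1 for 21 events in 266 person-years, and 5.2 to 12.1 for 24 in 296.

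**Routes that come near the stated pair, each departing from a stated input.**
- All 150 at risk, annual table: 150 × (1 + 0.72 + 0.5184) = 335.8 person-years, 26.9 events.
- All 150 at risk, year-end loss starting only after SVR12: 336.5 person-years and 26.9 events (20% of original cohort), or 340.2 and 27.2 (of those remaining).
- 135 at risk, no stop at reinfection, year-end loss: 135 × (1 + 0.8 + 0.6) = 324.0 or 135 × (1 + 0.8 + 0.64) = 329.4; 336.4 or 340.6 if loss starts only after SVR12.
- 20% treated as a total rather than per year: 135 × 3 / 1.2 = 337.5.

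**The case against.** The best defence is that the cohort at risk is not settled. The re-infection paragraph follows everyone with an end-of-treatment response, which the Abbreviations List defines differently from SVR12. With all 150 at risk and the stop kept, 336 person-years and 26.9 events come out of a simple annual table. This stands as a possible origin of the figures. It does not rescue the text, because the power sentence ties the 27 reinfections to 135 successfully treated participants.

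The same point rules out two stronger readings. A reader might infer that the stop at reinfection was simply forgotten, or that no cohort could give 27 events. The documents support neither. Several routes lead close to the stated pair and the plan does not show which was taken.

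A reader might also push power at 2.94 down to 67%. That needs the first 12 weeks to be free of reinfection, which conflicts with the plan's start of risk at end of treatment.

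On the interval, it is fair to say that the Poisson sentence is written for the analysis and that the difference is only 0.3 per 100 person-years in one limit. Even so, the printed limit is not what the plan's method gives. It is also fair that these are planning figures for a secondary objective and that the 150 is not derived from them.

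**Conclusion.** Both points hold. The interval error is firm: for 27 events in 337 person-years the exact Poisson upper limit is 11.7, with the lower limit unchanged at 5.3.

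The mismatch with 135 at risk is also firm across the conventions tried. The shortfall is about 29 to 81 person-years (337 − 308 and 337 − 256) and about 2.4 to 6.5 events (27 − 24.6 and 27 − 20.5). Which replacement figure is right cannot be settled from the documents, since it depends on the unstated loss rule.

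The range assumes a constant 8 per 100 person-years, no deaths and three full years of follow-up. The last scheduled visit, study week 156, is 144 weeks after the week 12 end-of-treatment visit. That lowers the two of-those-remaining figures, spread and year-end, from 266 and 296 to about 252 and 280 person-years.

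It would be wrong to conclude that the 2.94 was miscalculated, that the analysis method is faulty, or that the SVR12 objective is affected. Only the stated precision and power of the secondary objective change.

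**What to change.** In Section 10, Secondary Objective, Sample Size, do one of the following.

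- **Keep 27 events in 337 person-years.** Correct the upper limit to 11.7, and state the cohort at risk and the loss rule that give 337. If that cohort is not the 135, the power sentence must name the same one.
- **Restate for 135 at risk.** State whether the 20% is of those remaining or of the original cohort, when in the year it falls, and when it starts. Then give person-years, events, exact Poisson interval and detectable hazard ratio (or power at 2.94) together. As examples, with 20% of those remaining lost each year: 266 person-years, 21 events, interval 4.9 to 12.1, hazard ratio 3.4 (loss spread over the year); or 296, 24, 5.2 to 12.1, and 3.2 (year-end loss). These hazard ratios use the unrounded 21.3 and 23.7 events.

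If the event count changes, update the 27 in the re-infection paragraph to match. The sponsor should work out the sample total there, because that sentence counts every viral recurrence.

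The cost is a few lines of text and no extra patients. The downside is less favourable stated precision and power for the secondary objective.
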